# 10. SAFETY ANALYSES

Safety parameters will be listed and summarized for the primary safety population. The primary analysis of primary and secondary safety endpoints will be done using the primary safety population. Secondary analyses may be done using the other analysis populations defined in [Section 6](#) or in subgroups defined in [Section 7.4](#). Safety parameters are described below.

## 10.1 Primary Safety Endpoint

The primary safety endpoint is a composite indicator variable, as described in [Section 2.3.1](#). The primary safety endpoint listing will include indicators for each component of the endpoint and for the endpoint itself; similarly, each component and the endpoint itself will be summarized as frequency and percentage of subjects, 90% CIs for both treatment groups, a 90% CI for the difference in proportions between treatment groups, and the p-value from an equivalence Wald test of  $H_0$ .

Since the primary safety endpoint is based on events that occur immediately after IP infusion and safety analyses are done only in subjects who were infused, handling of missing data is not applicable.

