Point estimates and two-sided 95% confidence intervals for the proportion of subjects who experience any of the four events will be presented. Similarly, each of the four endpoints will be summarized separately with point estimates and two-sided 95% confidence intervals for the proportion of subjects who experience each event within the first month post-infusion. Also, two-sided 95% confidence intervals will be constructed for the difference between CAP-1002 and placebo and a two-sided Fisher Exact test will be used to compare the treatments for the Safety Analysis Set.

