## 2. STUDY OBJECTIVES, TREATMENTS, AND ENDPOINTS

### 2.1 Objectives

#### 2.1.1 Primary Objectives

The primary safety objective is to test the null hypothesis that the incidence rate of the primary safety endpoint (a composite of peri-procedural clinical events) differs by no more than 0.20 between treatment groups in subjects with ischemic left ventricular (LV) dysfunction and a previous MI receiving CAP-1002 or placebo by intracoronary infusion.

The primary efficacy objective is to test the hypothesis that, in subjects with ischemic LV dysfunction and a previous MI, CAP-1002 by intracoronary infusion is superior to placebo in reducing infarct size, expressed as a percent of LV mass, 12 months after infusion, either in all subjects combined or in subjects with recent MI (<= 90 days before infusion).

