### 2.3 Study Endpoints and Hypotheses

#### 2.3.1 Primary Safety Endpoint

The primary safety endpoint is whether or not any of the following adjudicated (see [Section 12](#)) events occur during the one month post intracoronary infusion:

1. Acute myocarditis possibly attributable to the investigational product (IP), diagnosed with consideration of clinical context, with or without a clinically indicated endomyocardial biopsy. In order to be considered related to the IP, humoral or cellular immune reaction specific to CAP-1002 must also be documented for subjects treated with CAP-1002, or a temporal relationship with IP administration must exist for subjects administered placebo. See [Section 12](#) for further information related to blinded adjudication by the Clinical Events Committee (CEC).
2. Death due to ventricular tachycardia or ventricular fibrillation defined as occurring with electrocardiogram (ECG) documentation of these arrhythmias during ambulatory ECG monitoring in an outpatient setting or during routine ECG monitoring while hospitalized.
3. Sudden unexpected death defined as occurring within one hour of symptom onset, or unwitnessed death in a person previously observed to be well within the preceding 24 hours without an identified cause.
4. Major adverse cardiac event (MACE), defined as the composite incidence of death, nonfatal recurrent MI, hospitalization with primary discharge diagnosis of heart failure, emergency room treatment for heart failure [ N-terminal pro-hormone brain natriuretic peptide (NT-proBNP)  $> 450$  pg/mL or brain natriuretic peptide (BNP)  $> 100$  pg/ml, with treatment including intravenous diuretic administration], LV assist device (LVAD) placement or heart transplant. Peri-infusion MI will be defined as presence of troponin or creatine phosphokinase MB isoenzyme (CK-MB) levels  $> 5$  times the upper reference limit during the 24 hours following infusion. These elevations must be accompanied by symptoms of ischemia  $> 20$  minutes in duration and ECG changes indicative of new ischemia (new ST-T changes or new left bundle branch block), development of pathological Q waves on the ECG, imaging evidence of new loss of viable myocardium, or new regional wall motion abnormality.

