### **2.3.2 Primary Safety Endpoint Hypothesis**

For the primary safety endpoint, the following hypothesis set will be tested:

$$H_0: p_c - p_p \geq 0.20$$

$$H_a: p_c - p_p < 0.20$$

where  $p_c$  and  $p_p$  are the proportions of subjects in the CAP-1002 and placebo treatment groups, respectively, who experienced the primary safety endpoint.  $H_0$  will be rejected if the upper limit of the 90% confidence interval (CI) for  $p_c - p_p$  is less than 0.20.

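### SAP 10.1 gives each component of the primary safety endpoint a p-value against a 20-point margin that SAP 2.3.2 sets for the composite only; for rare fatal events that p-value misleads or cannot be computed.

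*SAP*

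**What the plan says.** The primary safety endpoint (SAP 2.3.1) is met if any of four adjudicated "events occur during the one month post intracoronary infusion": acute myocarditis, death from ventricular tachycardia or fibrillation, sudden unexpected death, or MACE.

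SAP 2.1.1 attaches the 0.20 margin to the composite: "a composite of peri-procedural clinical events) differs by no more than 0.20 between treatment groups". SAP 2.3.2 then sets H0 as a difference of 0.20 or more. It defines the two proportions as those of subjects "who experienced the primary safety endpoint", and rejects H0 when the upper 90% confidence limit for the difference is below 0.20. It gives no hypothesis for any component.

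SAP 10.1 widens the scope. One sentence covers components and composite together: "each component and the endpoint itself will be summarized as frequency and percentage of subjects, 90% CIs for both treatment groups", followed by "a 90% CI for the difference in proportions between treatment groups, and the p-value from an equivalence Wald test of" H0.

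Protocol 9.5.1 treats the components differently: "each of the four endpoints will be summarized separately with point estimates and two-sided 95% confidence intervals". It adds a 95% interval for the treatment difference and a two-sided Fisher exact test, without saying clearly whether these extend to the components. It contains no margin test. SAP 14 reports no deviations from the protocol's methods.

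**The concern.** A margin says how large an excess one is prepared to leave unexcluded. Twenty percentage points was written for a composite of peri-procedural events. Nothing in either document argues that an excess of that size is a sensible reference for sudden death or arrhythmic death within one month.

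When the expected count is a handful at most, a test against 0.20 rejects almost regardless of what happens. The component rows of Table 14.3.1.1.1 would then show very small p-values. A reader used to p-values that test for a difference could misread them, or take them as evidence of safety for that event. SAP 10.1 provides no test of whether there is any excess at all. If no event occurs, which is quite possible for a fatal component over one month, the specified statistic does not exist.

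**Working it through.** **Inputs.** Margin 0.20 and a 90% interval (SAP 2.3.2). Wald test (SAP 10.1). Up to approximately 69 CAP-1002 and 34 placebo subjects in the Primary Randomized Cohort (Protocol synopsis, Study Population). The analysis set is infused subjects (SAP 6), so 12-month non-completion does not reduce these numbers.

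**Assumptions.** The SAP does not state the variance estimator or a continuity correction; I take the unpooled form with no correction. It names Wald for the test only; I use the same method for the interval.

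**The plan's own figures.** 103 × 2/3 = 68.7 and 103 × 1/3 = 34.3, which gives 69 and 34. The documents give no power calculation for the safety test. Protocol 9.2 does give an upper bound below 20% for zero events in 14 subjects: 1 − 0.05^(1/14) = 0.193, which reproduces.

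**Formulas.** With x events among 69 on CAP-1002 and none among 34 on placebo:

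- d = x/69
- SE = √[d(1 − d)/69]; the placebo term is zero
- upper 90% limit = d + 1.645 × SE
- margin p = Φ[(d − 0.20)/SE]

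**Results.**

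| CAP-1002 vs placebo | d | SE | 90% CI for difference | margin p | Fisher p, two-sided |
|---|---|---|---|---|---|
| 0/69 vs 0/34 | 0 | 0 | 0 to 0 | undefined | 1.00 |
| 4/69 vs 0/34 | 0.058 | 0.0281 | 0.012 to 0.104 | 2 × 10⁻⁷ | 0.30 |
| 5/69 vs 0/34 | 0.072 | 0.0312 | 0.021 to 0.124 | 2 × 10⁻⁵ | 0.17 |
| 9/69 vs 0/34 | 0.130 | 0.0405 | 0.064 to 0.197 | 0.043 | 0.028 |
| 10/69 vs 0/34 | 0.145 | 0.0424 | 0.075 to 0.215 | 0.097 | 0.028 |

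For example, nine events give (0.1304 − 0.20)/0.0405 = −1.72, so p = 0.043. Under the display rule in SAP 7.3, the rows with four and five events both print as <0.0001.

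**The zero-event row.** A 90% interval of 0 to 0 claims perfect knowledge. The bound that reproduces the Protocol 9.2 figure gives, for each arm alone, 1 − 0.05^(1/69) = 0.042 for CAP-1002 and 1 − 0.05^(1/34) = 0.084 for placebo.

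**How firm is nine?** It sits at the edge. With 68 infused on CAP-1002 the upper limit is 0.19995 and nine passes; with 67 it is 0.203 and the largest passing count is eight. Other methods give upper limits for nine against none of 0.219 (continuity-corrected), 0.211 (Newcombe) and 0.212 (Miettinen–Nurminen), all above the margin. Under the last two, eight against none still passes, at 0.194 and 0.195. The rows with four and five events are not near any edge.

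**The case against.** The strongest reply is that nothing is decided from these p-values. The only decision rule, in SAP 2.3.2, concerns the composite; SAP 10.1 merely summarizes the components. That is right. A reader might infer that the plan would certify nine sudden deaths against none as acceptable, but the documents attach no success criterion or claim to a component row.

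Nor does that example isolate the fault. MACE includes all deaths, so sudden deaths also enter the composite. If those nine were the only events, the composite would itself be 9/69 against 0/34 and would pass. Limiting the test to the composite would not change that; it reflects the width of the margin and the leniency of Wald with an empty placebo cell.

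A reader might also infer that an excess of deaths would be hidden or the DSMB misled. The documents do not support this. The same table row must show counts, percentages and an interval for the difference, which for nine against none excludes zero. SAP 10.3 requires a separate summary of treatment-emergent deaths with a between-group p-value. The DSMB sees unblinded safety data at least every six months and its Chair is notified of each SAE (Protocol 10.8). Its charts address a 10% absolute excess (Protocol 9.8.2), and SAP 13.2.1 describes the DSMB's 20% test for the primary safety endpoint only.

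It would also be too strong to say that every component row will show a small p-value: ten against none gives 0.097, and none against none gives nothing.

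Finally, Protocol 9.5.1 has no margin test for the composite either, so its silence alone does not single out the components. What does is SAP 2.3.2, which defines the margin hypothesis for the composite and nothing else. If the p-value was meant for the composite row only, the sentence in SAP 10.1 needs the same edit.

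**Conclusion.** The point holds as a fault in the specified table. As worded, SAP 10.1 tests each component against a 20-point margin that no part of the plan defines or justifies for components. For rare fatal components the result is uninformative or misleading (below 0.0001 at four or five events against none, and 0.043 at nine against none beside a Fisher p-value of 0.028) or does not exist (no events in either arm).

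The figures rest on 69 and 34 infused subjects, no placebo events, and an uncorrected, unpooled Wald calculation. The exact count of nine depends on all of these; the conclusion does not. The composite decision, the estimates and DSMB monitoring are unaffected. It should be corrected before the tables are produced.

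**What to change.** - In SAP 10.1, limit the test of the 0.20 margin to the composite.
- For each component, report counts, percentages, an exact or score interval for the difference (which keeps a sensible width when an arm has no events), and a two-sided Fisher exact test.
- Remove the margin p-value from the component rows of Table 14.3.1.1.1.
- Reconcile the 90% level in the SAP with the 95% level in Protocol 9.5.1, and record any remaining difference in SAP 14.

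The cost is one sentence in SAP 10.1, one table shell and, if the confidence levels stay different, a line in SAP 14. No new data are needed, and the sample size and the composite's decision rule do not change.

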## 10.2 Secondary Safety Endpoints

The secondary safety endpoints include clinical events, as described in [Section 2.3.3](#). The secondary safety endpoint listing will include indicators for each event, study day of the event, and total days of follow-up. Each endpoint will be summarized as frequency of subjects who experienced the endpoint and event rate per 100 subject-years. The summary table of the clinical event endpoints will also include a p-value for the comparison of event rate between treatment groups based on negative binomial regression with an offset for days of follow-up (log transformed). If the dispersion parameter is not significantly different from zero, Poisson regression will be used instead. Since the clinical event endpoints account for differential length of follow-up, handling of missing data is not applicable.

For the analysis of the secondary safety endpoint of development of increased HLA antibody levels to HLA antigens specific to the CAP-1002 CDC donor, incidence of increased HLA antibody levels, specific to the donor, will be summarized and analyzed; for placebo subjects, a random donor will be selected from those that were matched to the subject during screening. Elevated levels of DSA will also be summarized and analyzed by time point for all nominal time points at which samples were collected for DSA testing. Analyses will be performed using both 5000 and 1000 MFI as the threshold for defining increased HLA antibodies.

One secondary safety endpoint, new TIMI flow  $\leq 1$ , would only occur intra-procedurally and will be analyzed using a chi square or Fisher's exact test instead of negative binomial or Poisson regression.

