The secondary efficacy objective is to evaluate whether administration of CAP-1002 by intracoronary infusion may result in other left ventricular structural or functional cardiac benefits for subjects with ischemic left ventricular dysfunction and a previous MI. Also evaluations will investigate whether administration of CAP-1002 may result in clinical or biomarker benefits for subjects with ischemic left ventricular dysfunction and a previous MI.

Study Design:

In Phase 2, the Primary Randomized Cohort will enroll up to approximately 103 subjects with a previous myocardial infarction (MI) and resultant ischemic left ventricular dysfunction meeting all inclusion and no exclusion criteria. The Primary Randomized Cohort will include the Recent and Chronic MI strata (n= approximately 51-52 per stratum). These 103 subjects will be randomized in a double-blind fashion to receive either CAP-1002 or placebo (collectively referred to as Investigational Product [IP]) in a 2:1 ratio favoring CAP-1002 to achieve up to 93 subjects with complete 12 month data (assumes 10% non-completion rate and 103 subjects randomized). After completion of the screening procedures and meeting all inclusion and exclusion criteria, study subjects will be randomized to receive CAP-1002 or placebo administered via intracoronary infusion. All subjects in the Primary Randomized Cohort will be followed at week 2 and at months 1, 3, 6 and 12 after planned CAP-1002 or placebo infusion. Efficacy will be assessed at all specified post-infusion visits, with the 12 month visit being the primary efficacy endpoint. An administrative interim analysis of the final 6 month data will be performed when all subjects in the Primary Randomized Cohort have completed the 6 month visit to assist in planning Phase III studies.

The double-blind, placebo-controlled design of the Primary Randomized Cohort will maximize

the study's ability to assess both safety and efficacy, as both may be subject to bias from the perspective of Investigators and subjects.

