When fully enrolled, the ALLSTAR study will include a total of up to approximately 134 subjects with ischemic left ventricular dysfunction and a previous MI. Of these, up to approximately 83 will be treated (infused) with CAP-1002 (n=14 Safety Cohort, n=69 Primary Randomized Cohort) and up to approximately 34 will receive placebo (Primary Randomized Cohort only). Up to 17 subjects may be enrolled into the Phase II Exploratory Randomized Cohort. However, since this group is exploratory in nature, enrollment of the Primary Randomized Cohort will define the end of the study; that is, once the Primary Randomized Cohort is fully enrolled, the study will be considered closed for further subject enrollment.

Test Product, Dose, and Mode of Administration:

[REDACTED]

[REDACTED]

[REDACTED]

Inclusion Criteria:

1. History of MI (STEMI or NSTEMI) within the prior 12 months due to a coronary artery event and evidenced by at least two of the following: typical ischemic symptoms, serial ST-T changes (new ST elevation or new left bundle block) and/or elevated troponin or CK-MB >5 times the upper limit of normal. Also at least one of the following: development of pathological Q wave ECG changes, imaging evidence of new loss of viable myocardium, or new regional wall motion abnormalities.
 - The following assessments will be permitted within 28 days immediately following the subject's MI: signing ICF, review of medical history, review of concomitant medications, and collection of laboratory samples required for assessment of study eligibility criteria (e.g., eGFR, HbA1c, hepatitis serology, HIV serology, LFTs, hematocrit, WBC, and platelet count). All other screening tests, including the subject's cardiac MRI and CT (chest, abdomen, pelvis), must be conducted greater than 28 days post-MI. *Infusion must occur within 28 days of the first screening procedure that is performed greater than 28 days post-MI.* Relevant safety laboratory sample collections (e.g., chemistry, hematology, urinalysis) may need to be repeated as they must be obtained within 28 days of the subject's infusion.
2. History of percutaneous coronary intervention (PCI), with stent placement resulting in TIMI flow = 3, in the coronary artery supplying the infarcted, dysfunctional territory and through which the treatment will be infused.

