specific to CAP-1002), death due to ventricular tachycardia or ventricular fibrillation, sudden unexpected death, or a major adverse cardiac event (MACE), defined as the composite incidence of death, non-fatal recurrent MI, hospitalization for heart failure, emergency room treatment for heart failure (NT-proBNP >450 pg/mL or BNP >100 pg/ml, with treatment including intravenous diuretic administration), left ventricular assist device (LVAD) placement or heart transplant within the first month post-infusion will be calculated.

Secondary Safety Endpoints: Descriptive analyses of all secondary safety endpoints will be performed using percentages, means, and ranges where appropriate. For incidence rates, two-sided 95% confidence intervals will be constructed for the differences between CAP-1002 and placebo and a two-sided Fisher Exact test will be used for between-treatment comparisons; the Wilcoxon-Mann-Whitney test will be used to compare distributions and ordinal outcomes between randomized treatments. There will be no adjustments for multiple safety assessments by the DSMB and at the interim analyses; a two-sided $p=0.05$ will be used to establish statistical significance.

Primary Efficacy Endpoint: The primary efficacy endpoint is the percent change from baseline in MRI assessment of infarct size as a percent of left ventricular mass 12 months after administration of treatment (either CAP-1002 or placebo). The primary efficacy hypothesis is that CAP-1002 is superior to placebo in reducing infarct size in either all subjects combined (“full group”) or in subjects with recent MI (“subgroup”). A closed testing procedure will be used so that strong control of type 1 error is maintained.

The primary analysis will be a longitudinal mixed effects model. The response variable of percent change from baseline in infarct size as a percent of left ventricular mass will be modeled with the fixed categorical effects of treatment group and time (6 and 12 months), as well as a continuous fixed covariate of baseline infarct size. Intercept and subjects will be treated as random in this mixed effects model. The primary hypothesis will be tested using the estimated treatment effect compared to placebo at 12 months. An additional test will compare the treatments at 6 months and will be considered secondary. Model results will be provided for fixed affects and estimates for each level of each affect.

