## 7.3 Data Analysis

- The reference date used for summaries and analyses will depend on the analysis population, as follows:
  - ITT population: randomization date
  - mITT population: IP administration date
  - Safety population: IP administration date
  - Per protocol population: IP administration date
- Categorical variables will be summarized as frequencies and percentages in each category. Percentages will be reported to one decimal place. Unless otherwise noted in Sections 8-10, categorical variables will be analyzed using chi square tests of association or, if any contingency table cell has less than 5 subjects, Fisher's exact test.
- Continuous variables will be summarized by numbers of subjects, means, standard deviations, medians, and ranges. The number of decimal places for minimums and maximums will be the same as the original data. The number of decimal places for means, medians, and interquartile ranges will be the same as the original data plus one. The number of decimal places for measures of variance will be the same as the original data plus two. Unless otherwise noted in Sections 8-10, continuous variables will be analyzed using t-tests. Non-parametric tests and data transformations will be considered for variables with distributions that violate t-test assumptions.
- Data with qualifiers (e.g., “<”) will be listed with but summarized without the qualifier.
- P-values will be presented to two decimal places if  $> 0.01$ , to three places if  $< 0.01$  but  $> 0.001$ , and to four places if  $< 0.001$  but  $> 0.0001$ . P-values  $< 0.0001$  will be presented as “ $< 0.0001$ .”
- Statistical tests will be two-sided and tested at the 0.05 significance level unless otherwise noted in Sections 8-10.
- It is understood that statistical non-significance is not an indicator of equivalence.

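### SAP 10.2 replaces the protocol's Fisher test for most secondary safety events with a rate regression, declares no deviation, and has no rule for an arm with no events

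*SAP*

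**What the plan says.** **Protocol.** For incidence rates among the secondary safety endpoints, the Synopsis (Statistical Methods) plans two-sided 95% confidence intervals for the CAP-1002 minus placebo difference and says that "a two-sided Fisher Exact test will be used for between-treatment comparisons". A two-sided 0.05 "will be used to establish statistical significance", with no adjustment for repeated safety looks. Section 9.6.1 lists the same endpoints and names no test, so the body of the protocol does not contradict the synopsis.

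**SAP.** Section 10.2 reports the number of subjects with each event, the rate per 100 subject-years, and a "p-value for the comparison of event rate between treatment groups based on negative binomial regression with an offset for days of follow-up". It adds: "If the dispersion parameter is not significantly different from zero, Poisson regression will be used instead". No interval for the difference is planned. One endpoint is exempt: new TIMI flow of 1 or less "would only occur intra-procedurally and will be analyzed using a chi square or Fisher's exact test instead of negative binomial or Poisson regression". The anti-HLA endpoint has its own paragraph, which names no specific test. Section 7.3 sets a general default for categorical data of chi square or, "if any contingency table cell has less than 5 subjects, Fisher's exact test", but yields to anything stated otherwise in Sections 8 to 10. Section 14 reports no deviations from the protocol's statistical methods.

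**The concern.** The two documents give different tests for the same endpoints, and the section meant to record such changes says there are none. That needs correcting whichever test is preferred.

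The substituted method also suits these data poorly. The list in SAP 2.3.3 includes arrhythmic death, sudden death, myocarditis and new cardiac tumour. Several of these can happen only once per subject, and most should be rare. The placebo arm is small. If an arm has no events, the estimated log rate ratio runs to infinity and the large-sample p-value depends on which test is read from the output. SAP 10.2 neither names the test nor says what to do in that case. The result of a pre-specified safety comparison could then fall on either side of 0.05 for a reason unrelated to the data.

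**Working it through.** **Arm sizes.** The protocol synopsis plans "n=69 Primary Randomized Cohort) and up to approximately 34 will receive placebo (Primary Randomized Cohort only", with allocation "in a 2:1 ratio favoring CAP-1002 to achieve up to 93 subjects with complete 12 month data". Check: 103 × 2/3 = 68.7 and 103 × 1/3 = 34.3, which agrees with 69 and 34.

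**How likely is an empty arm?** The documents give no event rates, so the risks here are assumptions. The chance of no event among 34 placebo subjects is (1 − risk)^34:

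- 2%: 0.98^34 = 0.50
- 3%: 0.97^34 = 0.36
- 5%: 0.95^34 = 0.17

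The chance that exactly one arm is empty, when both arms have the same risk, is 50%, 39% and 19% respectively.

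**What each test gives.** Assume equal follow-up of 360 days and at most one event per subject. For k events on CAP-1002 and none on placebo:

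- Poisson likelihood-ratio statistic = 2k × ln(103/69), referred to chi square on 1 df. For k = 5 this is 10 × 0.4006 = 4.01, p = 0.045.
- Poisson Wald: the estimate diverges and its standard error diverges faster. For k = 10 the fitted log rate ratio is about 22 with a standard error of about 17,000, so p = 0.999.
- Exact conditional Poisson: binomial test with probability 69/103.
- Fisher: hypergeometric, two-sided.

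| Events, CAP-1002 (of 69) v placebo (of 34) | Wald | Likelihood ratio | Exact conditional Poisson | Fisher |
|---|---|---|---|---|
| 3 v 0 | 0.999 | 0.121 | 0.556 | 0.549 |
| 5 v 0 | 0.999 | 0.045 | 0.179 | 0.168 |
| 8 v 0 | 0.999 | 0.011 | 0.059 | 0.0501 |
| 9 v 0 | 0.999 | 0.007 | 0.035 | 0.028 |
| 12 v 0 | 0.999 | 0.002 | 0.012 | 0.008 |
| 0 v 3 | 0.999 | 0.010 | 0.036 | 0.034 |

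A negative binomial fit with dispersion fixed at 0.5 (an assumption) gives the same Wald values and nearly the same likelihood-ratio values (5 v 0: 0.047).

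**Is the likelihood-ratio value too small, or is Fisher merely conservative?** Take 5 v 0. Given five events and no treatment effect, the Poisson probability that all five fall on CAP-1002 is (69/103)^5 = 0.135. A two-sided p-value of 0.045 is smaller than the probability of that single outcome, so the chi-square approximation has failed.

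**The dispersion test.** A 0/1 outcome with mean p has variance p(1 − p), which never exceeds p. With near-equal follow-up there is no extra-Poisson variation for a negative binomial model to find, so for once-only events the choice between models rests on a quantity that is essentially not estimable. For events that can recur, dispersion exists in principle but would be estimated from a handful of repeats.

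**The case against.** The tempting stronger reading is that the SAP's method gives p near 1 whenever an arm is empty, so that the clearest safety signals will be reported as 0.999. The documents do not support this. SAP 10.2 does not say Wald, and SAP 7.1 names only the software. Likelihood-ratio, score and exact p-values from the same rate model are not near 1 for the larger imbalances. The statement is true only if Wald p-values are used.

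Nor would a signal be concealed. SAP 10.2 tabulates subjects with events and rates, and lists every event. SAP 10.3 adds incidence comparisons by system organ class and preferred term, including serious events and deaths, and Fisher is the default there for small cells. The DSMB charts in Protocol Appendix 3 rest on an exact test and may be used for any binary safety outcome.

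The large examples need 13% (9/69) or 17% (12/69) incidence on CAP-1002 with none on placebo. With fewer events Fisher is not significant either. In that direction it passes 0.05 only from 9 v 0 upward.

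A rate model also has a legitimate purpose. Cardiovascular hospitalization and ventricular tachycardia can recur, follow-up will differ (the protocol assumes 10% non-completion), and SAP 10.2 gives differential follow-up as the reason that missing data need no further handling. Fisher ignores both features.

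These arguments limit the consequence and shape the remedy. They do not answer the undeclared departure, the missing interval, the unstated test or the missing rule for an empty arm.

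**Conclusion.** The point holds in conditional form. SAP 10.2 departs from the synopsis's Fisher test and 95% interval for the clinical-event endpoints other than TIMI flow and anti-HLA sensitization, and Section 14 does not declare it. An empty placebo arm has a 17% to 50% chance at assumed risks of 5% down to 2%, and the SAP leaves that case undefined. The same 5 v 0 table could be reported as 0.999 (Wald) or 0.045 (likelihood ratio), against 0.168 by the protocol's test. Wald would mask an imbalance and likelihood ratio would overstate one. Choosing the model by a dispersion test adds nothing reliable.

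The conflict between the documents rests on their text alone. The sizes rest on arms of 69 and 34, equal 360-day follow-up, at most one event per subject, and illustrative risks. The SAP should be corrected, but these are secondary comparisons without multiplicity control, and the raw counts will be visible.

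**What to change.** In SAP 10.2, make the subject-level two-sided Fisher exact test, with a 95% confidence interval for the difference in proportions, the stated comparison for these clinical-event endpoints, as in the protocol synopsis. Delete the dispersion pre-test. Keep rates per 100 subject-years as description, and add an exact conditional Poisson test as a supportive analysis where follow-up differs or events recur.

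If the sponsor prefers to keep the rate model, declare it as a deviation in SAP Section 14 and specify an exact test for sparse tables or an arm with no events.

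The cost is SAP wording and simple programming, with no change to data collection or sample size. The downside is that repeat events and unequal follow-up are then handled only in the descriptive or supportive analysis.
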